5.4 Secondary analyses

We will undertake incremental cost-effectiveness analyses from mental health service perspective as secondary analyses. The outcome measure of secondary analyses was based on RCADS t-score.

First, we will use the RCADS t-score directly as in the clinical effectiveness analysis. The difference in RCADS t-score at 6 months (primary endpoint) will be estimated following the statistical analysis, using a mixed-effects generalised linear regression model. The model will adjust for RCADS at baseline and include trial group, group-by-time interaction and other baseline covariates as fixed effects, and participants and therapists as random effects to account for repeated measures within participants and possible clustering by therapist.

Secondly, we will calculate the reliable change index (RCI) for RCADS t-score, using standard deviation and Cronbach's α estimated from the pooled sample of both groups at baseline, along with 95% inclusion interval (Equation 1) (14, 15). The change is defined as reliable if the difference in RCADS t-scores between baseline and 6 months is larger than the estimated RCI, otherwise no reliable change. As lower t-scores on RCADS indicate better outcomes, the reliable change is referred to as reliable improvement when the change is deemed reliable and the score at 6 months is lower than at baseline.

Equation 1

$$RCI = SD \times \sqrt{2} \times \sqrt{(1 - \text{Cronbach's } \alpha)} \times 1.96$$

The proportion of participants who make reliable improvement in each group will be calculated. The difference between groups will be calculated by subtracting the proportion in the usual care group from the proportion in the ComBAT group.

The difference in costs of treatments (ComBAT and usual care) and other mental health specific services from baseline to 6 months follow-up will be estimated using generalised linear regression model.

These differences will be used to estimate the incremental costs of ComBAT, comparing with usual care, 1) to reduce one point on RCADS t-score, and 2) to achieve one case of reliable improvement by RCADS t-score.

5.5 Sensitivity analyses

A series of sensitivity analyses will be undertaken to assess the uncertainties of the conclusion. While the primary outcome is RCADS t-score, one of the eligibility criteria used RCADS depression subscale. We will therefore conduct a sensitivity analysis using RCADS depression subscale t-score for classification of non-clinical, borderline and clinical depression, instead of RCADS t-score.

To assess the impact of missing data, complete case analyses will be undertaken following the same approach of the primary analysis but only on those who have complete data on costs, QALYs, number of absent days and baseline covariates.

To examine the robustness of the MAR assumption, sensitivity analyses will be carried out using pattern mixture modelling (9). This method assumes that data are missing not at random (MNAR) and sets rules for imputing to reflect this assumption. In the current analysis, we will assume that those who have missing values at follow-ups either need more health care services or experience worse health (lower utility values and higher RCADS scores), or both at the same time. To examine how these scenarios will affect the results based on MAR assumption, the incremental costs and QALYs will be re-estimated based on data with 1) imputed costs are increased by 20%, 40% and 60%; 2) imputed QALYs are reduced by 20%, 40% and 60%; 3) imputed RCADS are increased by 20%, 40% and 60%; 4) the combination of 1) and 2); 5) the combination of 1) and 3).

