4.2.2 Quality-Adjusted Life Years

The Child Health Utility – 9 Dimensions (CHU-9D) (5) is used to derive health gain in quality-adjusted life years (QALYs). The questionnaire consists of 9 domains, each with 5 statements (scored 1–5) that assess the young person's functioning “today” across domains of worry, sadness, pain, tiredness, annoyance, school, sleep, daily routine and activities. For example: 1= I don't feel sad today, 2=I feel a little bit sad today, 3=I feel a bit sad today, 4=I feel quite sad today, 5=I feel very sad today. The responses under the 9 domains can be taken together as a description of the young person's “health state” that combines all responses across all items (e.g. 11232152). Different utility weights are assigned to each level of each domain. Different combinations of responses across the 9 dimensions therefore result in different health states that have a utility value on a 0–1 scale, where 1 is perfect health and 0 is equivalent to being dead. The UK young people valuation set will be used to derive the utility values (6).

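### SAP 5.5: the two RCADS scenarios of the MNAR analysis are read out on costs and QALYs, which follow-up RCADS does not enter, and the shifts are poorly scaled and never arm-specific

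*SAP*

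**What the plan says.** Section 5.5 sets out a pattern-mixture analysis under MNAR. Its premise is that "we will assume that those who have missing values at follow-ups either need more health care services or experience worse health", or both. It names what is recalculated: "the incremental costs and QALYs will be re-estimated based on data with 1) imputed costs are increased by 20%, 40% and 60" per cent. Scenario 2 is that "imputed QALYs are reduced by 20%, 40% and 60" per cent and scenario 3 that "imputed RCADS are increased by 20%, 40% and 60" per cent. The last two are "4) the combination of 1) and 2); 5) the combination of 1) and 3".

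Four other sections bear on this:

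- Section 4.2.2: the CHU-9D "is used to derive health gain in quality-adjusted life years (QALYs"), and each health state has "a utility value on a 0–1 scale, where 1 is perfect health and 0 is equivalent to being dead".
- Section 4.2.1: RCADS raw scores are converted to age- and gender-normed t-scores, with 70 or more in the clinical range. No maximum t-score is given.
- Section 5.3: incremental costs and QALYs come from regressions adjusted for baseline cost or baseline utility and other baseline covariates.
- Section 5.4: follow-up RCADS is the outcome of the secondary cost-effectiveness analyses (cost per t-score point and per case of reliable improvement at 6 months).

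Section 5.5 states no shift confined to one arm and no limit on shifted values. It does not say whether the QALY reduction applies to the whole QALY or to the imputed utilities behind it.

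**The concern.** A sensitivity analysis is informative only if the shifted quantity feeds the result that is read out. In scenarios 3 and 5 the shifted quantity is RCADS and the stated results are incremental costs and QALYs. Unchanged results from scenario 3 could be taken as robustness to MNAR when nothing had been tested, while the two RCADS-based ICERs, which these shifts would affect, have no stated MNAR check.

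The scale and direction of the shifts also matter. A percentage suits a quantity with a true zero, which a t-score lacks. A percentage of a whole QALY also alters the observed part. And the form of MNAR most likely to overturn a conclusion is that drop-outs do worse in one arm than in the other; no scenario is built to show that.

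**Working it through.** The SAP gives no figure on this point to reproduce. It also gives no missing rates, mean costs or mean QALYs, so those below are assumptions.

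**1. Does follow-up RCADS reach the stated results?** QALYs use the CHU-9D (4.2.2). Costs use resource quantities and unit costs (4.1). Covariates are baseline values (5.3). Section 5.5 shifts values that are already imputed, so RCADS cannot act through the imputation model either. Hence scenario 3 equals the MAR result and scenario 5 equals scenario 1. Five scenarios at three levels make 15 runs if combinations use matched percentages, and 2 × 3 = 6 of them add nothing. A simulated trial of 236 with RCADS shifted in about 30% of participants, with costs and QALYs each regressed on arm, shows the same. Incremental cost (189.13) and incremental QALY (0.0106) are identical at shifts of 0, 20, 40 and 60%. Only the RCADS difference moves, from −1.29 to −2.05.

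**2. Percentage shifts of a t-score.** 70 × 1.2, 1.4 and 1.6 = 84, 98 and 112. At +40%, every imputed score of 70/1.4 = 50 or more lands in the clinical range; at +60%, every score of 70/1.6 = 43.8 or more does. Were the read-out corrected, a further problem would remain. With an equal missing fraction m in both arms, and an imputed between-arm difference equal to the overall difference, a shift c multiplies the RCADS difference by (1 + cm). At m = 0.30 and c = 0.60 that is 1.18, so a scenario meant to be pessimistic would enlarge an apparent benefit of ComBAT.

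**3. Scaling a whole QALY.** Assume trapezoidal QALYs from months 0, 6 and 12 (weights 0.25, 0.5, 0.25), utility 0.8 throughout, and only month 12 missing. The observed part is 0.75 × 0.8 = 0.6. For a cut r, the implied month-12 utility is (0.8(1 − r) − 0.6)/0.25:

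| Cut | Implied month-12 utility |
|---|---|
| 20% | 0.16 |
| 40% | −0.48 |
| 60% | −1.12 |

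The last two lie below the 0–1 scale of section 4.2.2.

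**4. The same shift in both arms.** Let the mean QALY be 0.82 (ComBAT) and 0.80 (usual care), and the mean cost £1,200 and £1,000. The increments are then +0.020 and £200, and the ICER is £10,000. Assume imputed means equal the arm means. The QALY increment after the shift is 0.82(1 − c·m1) − 0.80(1 − c·m0), where m1 and m0 are the missing fractions in ComBAT and usual care. If m1 = m0 = m, this is 0.020 × (1 − cm), and the cost increment is £200 × (1 + cm). For a shift in ComBAT only, it is 0.82(1 − c·m1) − 0.80.

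| Missing, ComBAT / usual care | Arms shifted | 20% | 40% | 60% |
|---|---|---|---|---|
| 30% / 30% | both | +0.0188 | +0.0176 | +0.0164 |
| 30% / 20% | both | +0.0028 | −0.0144 | −0.0316 |
| 20% / any | ComBAT only | −0.0128 | −0.0456 | −0.0784 |
| 30% / any | ComBAT only | −0.0292 | −0.0784 | −0.1276 |
| 40% / any | ComBAT only | −0.0456 | −0.1112 | −0.1768 |

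Scenario 4 at 60% with 30% missing in each arm gives £236/0.0164 = £14,390, a 44% rise in the ICER. With 20% or 40% missing in each arm it gives £12,727 or £16,316.

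**The case against.** The best defence of scenarios 3 and 5 is that an output was left out by oversight. Scenario 5 pairs costs with RCADS, which is the cost-per-RCADS analysis of section 5.4, and the stated purpose is to see how the MAR-based results change. That is probably the intent, but the text names only costs and QALYs, so the output still has to be written in.

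A reader might infer more than the document supports, in three ways:

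- **That section 5.5 cannot test MAR at all.** Scenarios 1, 2 and 4 shift the inputs of the primary analysis, and with 30% against 20% missing the QALY increment changes sign.
- **That equal shifts in both arms cancel.** Exact cancelling needs the same missing fraction and the same imputed mean in both arms. Section 5.2 imputes by arm, so the means can differ, and with equal missingness the increments are rescaled rather than removed. The 44% rise in the ICER shows that this is not nothing.
- **That the shifts give impossible values generally.** Raised costs have no upper bound, and a reduced QALY total stays within 0–1 (0.80 becomes 0.64, 0.48 or 0.32). The SAP states no t-score ceiling, so 112 is implausible rather than shown to be impossible.

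The negative utilities also depend on one reading of an ambiguous sentence. The premise in section 5.5 speaks of lower utilities. If the imputed utilities themselves are scaled, they stay in range. Even on the whole-QALY reading, with both follow-ups missing a 60% cut implies a mean follow-up utility of (0.32 − 0.20)/0.75 = 0.16, which is in range. What stands is that the plan does not say which is meant.

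**Conclusion.** The emptiness of scenarios 3 and 5 follows from the text and needs no numerical assumption; the count of 6 runs in 15 assumes matched percentages. The RCADS-based ICERs have no stated MNAR check.

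The other three points are real but lesser or conditional. Percentage shifts of a t-score have no natural meaning. Negative implied utilities (−0.48 and −1.12) require whole-QALY scaling with only month 12 missing, utility 0.8 throughout and trapezoidal QALYs. That the sign cannot change holds when missingness is equal and imputed means follow the arm means; under the figures assumed above, a ComBAT-only shift reverses the sign even at 20%. Nothing here predicts what the trial will show.

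Severity: should be fixed. The primary MAR analysis is untouched, and scenarios 1, 2 and 4 retain some value.

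**What to change.** Revise section 5.5 before outcomes are analysed by arm, so that the choice of shifts cannot look data-driven:

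1. For scenarios 3 and 5, re-estimate the 6-month RCADS t-score difference, the difference in the proportion with reliable improvement, and the two ICERs of section 5.4.
2. Replace the percentage RCADS shifts with additive shifts in t-score points, kept within the instrument's range. State that range and justify the sizes, since the SAP gives neither.
3. Apply the QALY shift to the imputed utilities at the missing visit or visits, bounded by the CHU-9D value set, and then recompute QALYs.
4. Run every shift in both arms, in ComBAT only and in usual care only.

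The cost is a change of wording and about three times as many automated sensitivity runs (15 × 3 = 45 with matched combinations). No extra data are needed.
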